### **1.3 STUDY DESIGN**

**Scientific Questions and Impact:** School-aged children with intellectual & developmental disabilities (IDD) are at extreme risk for severe COVID-19. Many have compromised immunological and respiratory function, and their risk is compounded by high prevalence of communication disorders that can lead to impaired self-reporting of illness, as well as cognitive impairment and mobility issues that lessen compliance with safety protocols (distancing, masking, and sanitization). While some of these children are served in public schools, many are in IDD-specialized schools that provide not only educational services, but also clinical services, speech and psychological interventions, nutritional needs and physical care. For parents or guardians, the burden of homecare is enormous, such that maintaining employment is often impossible when the child is out of school. It is therefore essential that schools re-open in a manner that is safe for students with IDD. This project proposes a holistic virological and serological testing strategy, augmented by a mobile testing unit, systems modeling, educational outreach to address vaccine and testing hesitancy, and a scalable, innovative outcomes assessment that addresses multiple health domains (including anxiety, depression and social functioning), to stand up, refine and understand the best strategies for returning this vulnerable population safely to school. Our ultimate goal is to develop generalizable and scalable approaches that can be disseminated rapidly to facilitate school opening.

**Participants:** Rochester's Mary Cariola Center (**MCC**) serves moderate-to-severe IDD children (**N=450**) via a large professional and support staff (**N=500**). 70% of MCC students live in poverty, and 54% are from under-represented minority (URM) backgrounds. MCC is highly representative of similar settings across the nation. Here, we will build on the existing close partnership between MCC and the UR-IDDR, to implement and evaluate innovative testing strategies in this community that will prevent, contain and mitigate virus outbreaks – and maximize safe school participation for these vulnerable students.

**Scientific Goals:** We will use systems simulation modeling to develop an efficient virological and serological testing regime, and to optimize tracing and isolation processes. Longitudinal virological testing will track infection rates and serological testing will quantify durability of protective immunological responses, which may be shorter-lived in IDD populations. We will deploy an innovative mobile testing-unit for optimal testing flexibility. We will also address psychological barriers to full engagement with public health policies, including anxiety about COVID-19, as well as vaccine and testing hesitancy. To do this, we will develop effective support and educational outreach tools and strategies to mitigate these concerns. We will also establish a **community-engaged leadership plan** to direct this project, assure its sustainability, disseminate findings, and engage fully with all stakeholders (including the MCC community). We will work directly with the Coordination and Data Collection Center (CDCC) to facilitate full, accurate, rapid research data acquisition, curation and standardization, and deposit in the NIH RADx Data Hub. Our five goals are:

**1) Virological Testing:** We will establish a nasal-swab FDA-approved testing regimen to monitor and identify disease outbreaks in a specialized school setting serving 450 children with moderate-to-severe IDD and the 500 staff supporting them, a setting at ultra-high risk for COVID-19 disease transmission. We will rapidly identify infections and develop approaches for isolating and contact-tracing to stem virus spread. **2)**

**Serological Testing:** Serology will establish background immunity levels in students and staff, from infection or vaccination, and will follow those who are antibody-positive longitudinally to quantify temporal decay of IgG and neutralizing antibody levels. We will determine whether protective immunity in children with IDD, a population with prevalent immunological dysfunction, wanes at an accelerated rate compared to the population-at-large; by doing so we will address an important knowledge gap, and provide key data to inform public health policy. **3) Modeling to Optimize Testing:** We will use network models and agent-based simulation models (or hybrid approaches) to guide testing strategies and interventions at MCC. Simulations will be conducted interactively and iteratively, to assist in planning and implementation of testing procedures, exploring the dynamic interplay between school operations and personnel interactions, potential infection risks and disease dynamics (including variant strains), and implementation of control measures (e.g. quarantine, isolation, contact-tracing and vaccination rates). **4) Mobile Unit Testing:** We build on our successful mobile approach to delivering mobile dental care to the IDD students of MCC (the SMILEmobile), by staffing, equipping and deploying a customized, disability-enabled, mobile testing unit equipped with a specialized HEPA-filter enabled HVAC system (**UR Health in Testing - HIT Mobile**). We will use this to directly deliver rapid flexible testing to MCC. **5) Overcoming Testing & Vaccine**

**Anxiety/Hesitancy:** We will conduct focus group interviews at MCC to identify key community concerns, myths and misconceptions about vaccination, and we will then build on our success in reducing vaccine hesitancy among URMC staff, to create a multimodal educational campaign that addresses these concerns. Strategies will include a speakers' bureau, group discussions, and "table talk" conversations, combined with innovative visual approaches that communicate complex information in a readily accessible manner (via graphic medicine) and that promote vaccine uptake (via narrative portraits of trusted peers and coworkers who have chosen to be vaccinated). Finally, we will assess the impact of this program by deploying a validated, electronic patient reported outcome scale (PROMIS-29) already in widespread use across the UR health system and at Rochester's East High School, to collect longitudinal data from staff, parents/guardians and children (by proxy reporting) across multiple health domains (including anxiety, depression, sleep disturbance, and social functioning). This scalable approach will reveal the full impact of the interventions and approaches proposed, and is readily compatible with extension to other sites in the RADx network.

**Testing Capacity:** Our Clinical Microbiology laboratory began SARS-CoV-2 molecular testing on 3/16/2020, and has now tested over 500,000 specimens, with consistent turn-around times of 24-48 hrs. Current capacity is approximately 10,000 tests/day. High throughput SARS-CoV-2 molecular platforms include: COBAS 8800 (Roche), Panther (Hologic), GeneXpert (Cepheid), and Amplitude (Thermo-Fisher), among others. The lab has sufficient capacity to run all testing in-house and does not currently utilize reference testing (**Table 1**). Serological testing (IgG) has been available since 6/20 on the Abbott Architect. Available capacity greatly exceeds the needs of the present project; ***the project testing engine will be ready to start on day one of the project (i.e., as soon as the first participant is enrolled).***

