**Clinical Serological Testing:** Tests with FDA-EUA will be used to assess the presence of IgG antibodies to SARS-CoV-2 (Table 1) every 6 months. Our current Abbott Architect assay qualitatively assesses IgG binding to the SARS-CoV-2 nucleocapsid (NP) protein and we intend to offer the Architect anti-spike (S) semi-quantitative assay when it is granted EUA (expected shortly). Serum will be collected upon enrollment and then every 6 months for the duration of the study period. Assuming 70% study enrollment, this will result in 1,680 staff and 1,330 student serological tests.

[figure not shown]
**Reporting and Result Handling:** The ordering provider ([name]) at the MCC and nursing staff will receive test results. Positive results will be reported to public health agencies via standard clinical protocols. Both molecular and serological *clinical* results will be qualitative (Positive, Negative, Inconclusive). Upon the communication of a positive molecular test result, students and staff will be referred to their primary care providers (PCPs) or urgent care if lacking a PCP. Enrolled study subjects who have been in close proximity to the positive individual will be immediately PCR tested. Unenrolled, exposed individuals will be offered study enrollment or else referred to their PCP/urgent care for testing. RT-PCR positive students will be re-tested every two weeks to assess viral load kinetics.

**Research Serological Testing:** Modeling requires continuous, quantitative data to estimate antibody persistence, and as a correlate of immunity. We will test 200 subjects every 4 weeks for up to 36 months using a multiplex research assay that simultaneously measures IgG levels against the spike (S) and nucleocapsid (N) proteins of SARS-CoV-2 and human seasonal strains (OC43, HKU1, NL63, 229E); we will also measure antibodies directed against the receptor binding domain (RBD) of the S protein. This assay provides absolute measures of serum IgG (ng/ml), and is currently in use in several NIH funded studies (see Fig 1). We are also adding emerging SARS-CoV-2 variants (e.g. UK, South African). Samples will be collected by fingerstick and volumetric micro-sampling (VAMS) to collect 40 $\mu$ l of capillary blood. A topical anesthetic cream can be used prior to collection. Samples will be analyzed by batch in [name] lab.

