### Scientific Goal 2: Serological Testing and Modeling

The dynamics of the immune response to SARS-CoV-2 are as yet unknown in children with IDD, a population with prevalent immunological dysfunction, who may show different COVID-related immunological profiles and latencies to those of the general population. Here, we longitudinally follow those with IDD identified as antibody-positive, from either infection or vaccination, to quantify the timing of reductions in IgG and neutralizing antibody levels. We will use a combination of the SARS-CoV-2 clinical serological assay (described above), and a research multiplex assay for anti-spike and nucleocapsid protein IgG and receptor binding domain (RBS) antibodies, against SARS CoV-2 (including emerging virus variants), and a panel of commonly circulating human coronaviruses. *This will provide serological data uniquely focused on the IDD population with clear implications for public health immunity strategies.*

**Experimental Approach.** IgG responses to individual SARS-CoV-2 antigens (S, NP, RBD) in enrolled students and staff will be measured initially by clinical testing and fingerstick at baseline, and then every four weeks by fingerstick for up to 36 months. Any large increase in anti-SARS-CoV-2 levels will be confirmed by clinical serology. Dynamics of anti-SARS-CoV-2 IgG will be assessed by fitting the anti-S, NP and RBD quantitative results to a modified power law model that accounts for long-term antibody persistence:  $f(t) = k + \log [(1 - \lambda)(c + t)^{-\alpha} + \lambda]$ , where  $k$  is the peak log IgG level,  $\alpha$  is the decay rate,  $c$  is a constant, and  $\lambda$  is the steady-state long-term IgG level. We will fit the model using a mixed effects

**Figure 1 – Serological Testing.** (A) Clinical analysis of persistence of anti-S, anti-NP, and anti-RBD binding IgG and PCR results from the URMC Clinical Laboratory. Note the early decline of anti-NP IgG. (B) Multiplex testing for IgG directed against S proteins for common circulating coronaviruses, including SARS-CoV-2 (SARS2), and prior SARS-CoV-1 and MERS (Middle East Respiratory Virus)

method, where  $k$  and  $\alpha$  are subject specific random effects drawn from a bivariate normal distribution. This will allow comparison of decay rates ( $\alpha$ ) and steady state anti-SARS-CoV-2 IgG levels ( $\lambda$ ) across subjects.

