**Principal Investigator:**

**[name]**

**Department of Neuroscience**

## **DATA and STATISTICAL ANALYSIS**

Primary data analysis will focus on understanding the spread of COVID-19 in a school for children with Intellectual and developmental Disabilities. By testing both students and staff in the school, and understanding interactions of staff and students throughout the day we aim to understand risk and develop risk mitigation techniques to help the school better reduce outbreaks and risk of infection. Based on blood samples we will also study the immune response of students and staff both to vaccination and also to infection. The time course of the immune response will be evaluated. Information about immune responses and infection will be conveyed to families and staff in order to encourage vaccination and also to help them understand how they may be putting their students and families at risk. Longitudinal and regular virological testing will track infection rates, and serological testing will quantify the durability of protective immunologic responses, which may be shorter-lived in IDD populations.

Statistical analyses will be performed using SPSS, or other similar software. Descriptive statistics will describe the incidence rates of COVID infection in participants, and the immunity levels of the students and staff (based on serological testing). Network modelling and agent-based simulations will be used to interactively test mitigation strategies. Qualitative surveys of participants will facilitate understanding of key community concerns, myths, and misconceptions about vaccination, with a goal of developing a multimodal educational campaign that addresses these concerns.

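### Decay of neutralizing antibody and durability of protection are promised, but no described assay measures neutralization and no planned analysis relates IgG to later infection

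*Protocol*

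**What the plan says.** **Promises.** Protocol 1.3, goal 2 (Serological Testing), says the study "will follow those who are antibody-positive longitudinally to quantify temporal decay of IgG and neutralizing antibody levels". It goes on: "We will determine whether protective immunity in children with IDD, a population with prevalent immunological dysfunction, wanes at an accelerated rate". The opening paragraph of Scientific Goals in 1.3 also says serology will quantify how long protective responses last. Scientific Goal 2 in section 1.4 repeats the aim "to quantify the timing of reductions in IgG and neutralizing antibody levels". The SAP says "serological testing will quantify the durability of protective immunologic responses, which may be shorter-lived in IDD populations".

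**Measurements.** Scientific Goal 2 relies on two assays, both described in 1.4.
- Clinical serology: "Our current Abbott Architect assay qualitatively assesses IgG binding to the SARS-CoV-2 nucleocapsid (NP) protein". For spike, "we intend to offer the Architect anti-spike (S) semi-quantitative assay when it is granted EUA".
- Research serology: a "multiplex research assay that simultaneously measures IgG levels against the spike (S) and nucleocapsid (N) proteins of SARS-CoV-2", with antibodies against the RBD also measured.

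Section 4.1 adds memory B cell recall work, which the blood-draw table lists as a single draw.

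**Analysis.** Scientific Goal 2 fits a mixed-effects power-law model to the quantitative anti-S, NP and RBD results. The SAP plans descriptive statistics for immunity levels and says the time course of the immune response will be evaluated. It does not mention neutralizing antibody.

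**The concern.** The objectives name neutralizing antibody alongside IgG, as a quantity of its own, so a reader expects a separate measurement. They also promise a conclusion on protection, which is a statement about infection risk and not about antibody concentration.

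If the plan is followed as written, the first quantity has no data source and the second rests on an assumption that the study does not test. The assumption matters more than usual here. The protocol describes prevalent immunological dysfunction in this population and says its immune dynamics are still unknown, so a relation between binding level and protection seen elsewhere may not carry over.

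A faster fall in binding IgG could then be read as a faster loss of protection. The protocol intends the result to inform public health policy, and the SAP says information on immune responses will go to families and staff.

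**Working it through.** There is no figure in the plan to reproduce. The check sets each promised quantity against every assay and analysis that the documents describe.

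| Quantity promised | Where | Assay that yields it | Planned analysis |
|---|---|---|---|
| Decay of IgG | 1.3 goal 2; 1.4 Scientific Goal 2 | Multiplex (S, N, RBD) | Mixed-effects power-law model |
| Decay of neutralizing antibody | The same two places | None | None |
| Durability of protection | 1.3 opening of Scientific Goals; 1.3 goal 2; SAP | None directly; IgG is called a correlate of immunity (1.4, Research Serological Testing) | No threshold; no analysis of infection against IgG |

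Assay by assay:
1. *Clinical assay (1.4 and Table 1).* Qualitative binding IgG to NP, with a semi-quantitative anti-spike assay intended. Table 1 lists one serology platform. No functional readout is described.
2. *Research multiplex (1.4).* It "simultaneously measures IgG levels against the spike (S) and nucleocapsid (N) proteins of SARS-CoV-2" and of seasonal strains, plus antibodies to the RBD. These are concentrations of antibody that binds an antigen.
3. *Memory B cell work (4.1).* IgG specificities after culture, and ELISpot counts of antibody-secreting cells. It does not measure neutralization, and a single draw cannot give a decay curve.
4. *Blood-draw table (4.1).* Draws are assigned to COVID antibodies, memory B cells and DNA. None is assigned to neutralization.
5. *Decay model (Scientific Goal 2).* The inputs are anti-S, NP and RBD results only.

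The count is therefore two statements promising neutralizing antibody, with no assay and no model variable, and three promising protection, with no threshold and no analysis that defines or tests it.

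The planned data could still support a direct look at protection. Research Serological Testing schedules quantitative IgG every 4 weeks (28 days) for up to 36 months. Sections 1.4 and 4.1 schedule surveillance PCR every 5 to 14 days. Between two consecutive fingersticks that is 28/14 = 2 to 28/5 = 5.6 scheduled PCR tests per person. The schedule can thus place a new infection in time relative to the last IgG reading, but neither document plans to use it this way.

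**The case against.** The strongest defence is that the operational plan is already confined to binding antibody. Scientific Goal 2 models anti-S, NP and RBD results and compares decay rates and steady-state IgG, and the SAP never mentions neutralization. This stands. A reader might infer that Goal 2 as a whole cannot be met; the documents do not support that, because IgG decay has both an assay and a model.

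A second defence is that immunity is linked to infection in the modelling. Scientific Goal 3 stores PCR and serology results in one database, feeds rates of prior infection and vaccination derived from serology into the network models, and gives simulated agents an infection susceptibility. So it would be wrong to say that the plan ignores the relation between immunity and spread. But these are inputs to simulations. They do not estimate how a participant's measured IgG relates to that participant's later risk of infection.

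A third defence is that RBD antibody stands in for neutralization. The protocol does not say so and gives no conversion.

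In the other direction, a reader might infer from the volume of planned IgG readings that a protection analysis would be precise. The documents do not support this either. Precision depends on the number of infections, which they do not project. The schedules describe planned data and do not show that the data were retained. The number with monthly readings is also not uniform: Research Serological Testing gives 200, whereas Scientific Goal 2 and section 4.1 describe fingersticks in enrolled students and staff generally.

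**Conclusion.** The concern holds in a limited form. Decay of binding IgG can be estimated as planned. Decay of neutralizing antibody cannot, because nothing described in either document measures it. A conclusion that protection wanes faster in children with IDD cannot be drawn as designed, because the only bridge from IgG to protection is an assertion.

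The size of the problem is one of the two antibody quantities named for Goal 2, plus the interpretation placed on the other. It is a matter of what may be claimed and puts no bias into the IgG decay estimates. The verdict assumes that the assay descriptions in sections 1.4 and 4.1 are complete; they are specific and show no sign of removed text. It does not assume that binding IgG fails to track protection in this population, only that the study as planned would not show whether it does.

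**What to change.** 1. In Protocol 1.3 goal 2 and in 1.4 Scientific Goal 2, delete the word neutralizing and state the quantity as decay of binding IgG to S, NP and RBD.
2. In the opening of Scientific Goals in 1.3, in 1.3 goal 2 and in the SAP, replace protective immunity or responses with binding antibody.
3. Add one secondary analysis to the SAP: time to a new PCR-positive infection episode, modelled on the most recent IgG level as a time-varying covariate. Stratify or adjust for calendar time, adjust for vaccination and prior infection, and include a student/staff term. Give separate estimates for students and staff only if the number of events allows.
4. State a rule that counts repeat positives from one infection once. It is needed because positive students are retested every two weeks (1.4, Reporting and Result Handling), and the adverse-event definitions allow for positivity beyond 30 days.
5. Make statements about protection only from that analysis, with its confidence interval.

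If the sponsor prefers to keep the neutralization aim, the protocol would have to name an assay, the subset, the time points and the model. The documents do not establish whether suitable serum remains.

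**Cost.** Wording in four places (two with neutralizing, three with protective, one of them shared: 2 + 3 - 1 = 4) and one added analysis of planned data. No new assay or visit is needed. The downside is a narrower claim than is now promised, and a protection estimate that may be imprecise if infections are few.

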#### **Asymptomatic Testing –**

**Nasal Swab:** Participating individuals (students and employees) will be tested for COVID-19 (RT-PCR) using a specimen collected using a mid-turbinete swab. This asymptomatic testing

STUDY #: 5294

Version Date: 04/17/2023

Page 13 of 27

regime starts on or after (if scheduling testing requires this to begin on a different day) enrollment and is repeated every 5-14 days for up to 36 months. Anyone testing positive is followed up as described below for symptomatic individuals.

**Saliva Sample:** For those participants (students only) that are unable to tolerate the nasal swab (mid-turbinate) test, we will use the Spectrum Solutions™ SDNA-1000 Molecular Diagnostic Saliva Collection Device. This is a self-contained, **EUA authorized** saliva collection system. It requires filling a small tube with saliva.

**Blood Samples:** Participating asymptomatic individuals (students and employees) will be tested for antibodies using the fingerstick upon scheduling first sampling visit and monthly thereafter for up to 36 months. This first blood sampling will be using a fingerstick and 1-2 drops of blood will be collected in a curette for serology testing. Possible complications include pain from the fingerstick, and a low risk of infection. The rationale for this intervention is to measure serum antibodies against SARS-CoV-2 using standard FDA approved testing methods.

A second method for blood sampling using venipuncture will be carried upon enrollment or upon scheduling the first sampling visit and subsequently, every six months for up to 36 months. In addition this method will be used for additional blood collection for MBC and DNA analyses. This second method will use venipuncture to collect ~6-10 cc of whole blood (except in students younger than 5 years in whom we will collect between 3-5cc). The possible complications of phlebotomy/venipuncture include pain, small local hematoma formation, bleeding and infection. However, this method of blood collection and testing is widely used by millions individuals daily in the United States with minimal complications, including IDD subjects. Phlebotomy will be conducted by a team specially trained in working with IDD subjects to minimize risk.

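### The documents disagree on whether antibody decay is studied in all participants or only in antibody-positive ones, and the positives-only reading would bias the decay rate

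*Protocol*

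**What the plan says.** Two places describe the decay cohort by antibody status. The serology goal in protocol section 1.3 says the study "will follow those who are antibody-positive longitudinally to quantify temporal decay of IgG and neutralizing antibody levels". The opening paragraph of Scientific Goal 2 in section 1.4 says "we longitudinally follow those with IDD identified as antibody-positive, from either infection or vaccination".

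Two other places describe sampling with no serostatus condition. Under Experimental Approach in the same goal, IgG "in enrolled students and staff will be measured initially by clinical testing and fingerstick at baseline, and then every four weeks by fingerstick". In section 4.1 (Asymptomatic Testing, Blood Samples), participating asymptomatic students and employees "will be tested for antibodies using the fingerstick upon scheduling first sampling visit and monthly thereafter for up to 36 months".

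A fifth place limits numbers without saying who is chosen. Research Serological Testing in section 1.4 states "We will test 200 subjects every 4 weeks for up to 36 months using a multiplex research assay".

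The decay model is a modified power law with peak level k and decay exponent alpha as subject-specific random effects from a bivariate normal distribution. The origin of t is not stated. The SAP says only that the time course of the immune response will be evaluated. It names no analysis set, time origin or method for people who enter already positive.

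**The concern.** For anyone exposed before enrolment, being antibody-positive at entry is itself a result of slow decay or a high peak. A cohort restricted to people found positive leaves out those who have already waned below the cut-off. This is left truncation on the outcome being estimated, and nothing in either document corrects for it.

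Section 1.3 asks whether immunity wanes faster in children with IDD than in the population at large, and offers the answer as input to public health policy. A biased alpha weakens that answer. A comparison between groups is also exposed when the groups differ in time since exposure, because the more recently exposed group has lost fewer fast waners. Such a gap between students and staff is plausible: Contingency Plans expects vaccine approval for children under 16 only during the study.

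**Working it through.** **No planned figure to reproduce.** The documents give no sample size, effect size or variance for the decay analysis, so the size of the problem has to be illustrated under assumptions.

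**Who could be in the cohort.** At the 70% enrolment in section 2.1, 0.70 × 500 = 350 staff and 0.70 × 450 = 315 students, or 665 people. The research assay covers 200 of them, with no selection rule. Antibody positivity is the only criterion stated anywhere for decay follow-up.

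**How truncation acts.** The protocol's curve is f(t) = k + log[(1 − lambda)(c + t)^(−alpha) + lambda]. Assume lambda = 0.02, c = 1 month, k = 0 (the mean log peak) and t = 12 months:
- alpha = 0.6: log(0.98 × 13^(−0.6) + 0.02) = log(0.230) = −1.47
- alpha = 1.0: log(0.98/13 + 0.02) = log(0.095) = −2.35
- alpha = 1.4: log(0.98 × 13^(−1.4) + 0.02) = log(0.047) = −3.06

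With a cut-off 2.5 log units below the mean peak, the first two people are still positive at enrolment and the third is not.

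**Simulation, 400,000 people per scenario.** All parameters are assumptions: lambda and c as above, alpha with mean 1 and SD 0.4, SD of k 1.0 (natural log), assay SD 0.25, exposure 1–12 months before enrolment, and cut-offs 3.0, 2.5, 2.0 and 1.5 log units below the mean peak. Bias is (mean alpha in those positive at entry ÷ mean alpha in everyone) − 1. It measures selection only, not fitting error.

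At zero correlation between k and alpha, 83%, 72%, 58% and 43% are still positive at the four cut-offs, and the bias is −6%, −9%, −13% and −18%. Over the same cut-offs:

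| Correlation of k and alpha | Bias in mean alpha |
|---|---|
| −0.5 | about −11% to −27% |
| 0 | −6% to −18% |
| +0.5 | about −1% to −5% |
| +0.8 | about 0% to +9% |

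A second set of assumptions gives a similar span, −27% to +8% overall and −1% to −20% at zero correlation. It used SD of k 0.8, SD of alpha 0.2 or 0.4, 0–6 or 0–15 months since peak, cut-offs 1.5 or 2.5, and correlations −0.5 to +0.8.

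**Responses that begin under observation.** These carry no such selection, so the bias scales with the share already present at entry. If half the responses are incident, −18% becomes 0.5 × −18% = −9%. If three quarters are, it becomes 0.25 × −18% = −4.5%.

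**Group comparisons.** With equal true alpha, and groups exposed 1–4 versus 6–12 months before entry, the false difference in alpha is about 0.07 to 0.16 at zero correlation, 0.03 to 0.13 at +0.5, and near zero at +0.8. The recently exposed group appears to wane faster. With a true difference of 0.30 and the same exposure timing in both groups, the observed difference at zero correlation is 0.27 to 0.28, so it keeps 90% to 93% of its size (0.27/0.30 and 0.28/0.30).

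**The case against.** The best defence is that the operational text never makes positivity a condition of follow-up. The positivity sentences are summary and rationale. The paragraph that specifies the model fit, and the procedures in section 4.1, sample enrolled people from baseline. RT-PCR every 5–14 days dates new infections, large antibody rises are confirmed by clinical serology, and new vaccinations are expected. Many responses will therefore be seen from their start and cannot be lost beforehand. All of this stands. It does not settle who is analysed: sampling everyone is compatible with fitting decay only in positives, and two statements of the goal say that positives are the group followed.

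Several stronger readings are tempting, and the documents do not support them:
- **That the decay rate will be underestimated.** The model lets k and alpha correlate, and a strong positive correlation can remove or reverse the bias. The mix of prevalent and incident responses is also not given.
- **That the selection hides faster waning in children with IDD.** With equal exposure timing, most of a true difference survives. With students exposed 1–4 months and staff 6–12 months before entry, a true 0.30 appears as about 0.36 to 0.44 at zero correlation, which is exaggeration.
- **That entry is screened on anti-NP, the antigen the Figure 1 note marks as falling early.** The current clinical assay does target anti-NP, but no section makes it the gate. Baseline includes the fingerstick assay for S, NP and RBD. Section 1.4 treats vaccine responders as anti-NP negative, yet Goal 2 counts positives from vaccination.
- **That the student-versus-staff figures carry over to the stated contrast.** Section 1.3 compares with the population at large, and how that comparator is selected is not described.

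**Conclusion.** The point holds as an unresolved inconsistency with a quantifiable risk, not as a demonstrated bias in a known direction. Two statements of the goal follow antibody-positive people, two operational sections sample regardless of serostatus, and neither document defines the analysis set, time zero or the treatment of people already positive at entry.

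If the positivity rule is applied, alpha is biased for responses present at entry: about -6% to -18% with peak and decay uncorrelated, and about -27% to +9% over correlations of -0.5 to +0.8. Underestimation is the likelier direction. A spurious or inflated group difference is possible where exposure timing differs. These sizes rest entirely on the assumed parameters. If all responses began under observation, or people were analysed whatever their baseline serostatus, this selection would be absent. The plan should be changed because the question is a headline aim and the better definition uses procedures already in the protocol.

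**What to change.** Reconcile section 1.3 and the opening of Goal 2 with the Experimental Approach and section 4.1, and state how the 200 research-assay subjects are chosen. In the SAP:

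1. Define the primary decay cohort by a dated exposure, either first positive study PCR or recorded vaccine dose, whatever the antibody result at enrolment.
2. Count t from that date.
3. Keep all later continuous IgG values, including those from people who fall below the positivity cut-off. Treat values below the assay limit as left-censored in the mixed model.
4. Analyse people positive at baseline without a dated exposure separately, or condition the likelihood on positivity at entry. The second option needs a stated assumption about their exposure dates.
5. Report the numbers of prevalent and incident responses by group.

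The cost is SAP wording and a censored-data likelihood. No visits are added: the PCR schedule, monthly fingersticks and continuous assay are in the protocol, and Contingency Plans has vaccination recorded, provided the record carries the dose date. The downside is a somewhat smaller primary cohort, because undated seropositives move to a secondary analysis.
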